### 946 **5.3 Primary Analysis – Symptom Success at One Year**

947 For each of the modality/condition groups, the primary analysis will be an estimation of the  
948 proportion of patients of patients with treatment success based on improvement of symptoms at  
949 10 weeks post intervention and at one year, with 95% confidence intervals.  
950

951 Table 4 shows the criteria for symptom success for each condition, which will be used to assess  
952 all treatment modalities.  
953

954 **Table 4: One-Year Symptom Success Criteria for Each Condition**

Condition	One-Year Symptom Success Criteria
CI	improvement of CI Symptom Survey (CISS) score of at least 9 points AND a score of <21 points
DI	diplopia no more than rarely in the past week in the primary position (question #1.1 on the Diplopia questionnaire)
HT	diplopia no more than rarely in the past week both in the primary position and for reading (questions #1.1 and #1.2 on the Diplopia questionnaire)

955 For patients who initiate a new treatment before completing one year of follow-up, the symptom  
956 success/failure status from the visit at which treatment was changed (i.e., the 10-week interim  
957 visit or an early outcome visit) will be brought forward as their one-year outcome.  
958

960 Rubin's multiple imputation will be used to impute outcome for patients who have not changed  
961 treatments but who are lost to follow-up or withdraw from the study prior to one-year  
962 exam.

963

#### 964 **5.4 Secondary Analysis – Motor Success at One Year**

965 For each surgery type within a condition, a secondary objective will be to calculate the  
966 proportion of patients with motor success at one year and a 95% confidence interval. Motor  
967 success will be defined as orthotropia by cover/uncover at distance and near fixation in primary  
968 position at one year. Similar to the primary analysis of symptom success, for patients who  
969 change treatments before completing one year of follow-up, the motor success/failure status from  
970 the visit at which treatment was changed (i.e., the 10-week interim visit or an early outcome  
971 visit) will be brought forward as the one-year outcome. In addition, Rubin's multiple  
972 imputation will be used to impute outcome for patients who have not changed treatments but  
973 who are lost to follow-up or withdraw from the study prior to one-year exam.

974

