310 their treatment modality is changed during the study.

311

312 Outcome

313 The primary outcome will be symptom success at the 10-week and 12-month visit, defined as  
314 improvement of CI Symptom Survey (CISS) score of at least 9 points and an outcome score of  
315 <21 points. For surgical treatment, a secondary, motor outcome will evaluate how often subjects  
316 have become orthotropic at distance and near after treatment.

317

318 1.5.2 Study Flow Chart: CI

319

[figure not shown]
320

321

322

323

324

325 **1.5.3 Synopsis of Study Design for DI**

326 **Major Eligibility Criteria (see section 2.2.2 for full details)**

- 327 • Adults  $\geq$ 18 years of age
- 328 • Adult-onset DI (at  $\geq$ 18 years of age)
- 329 • No prior strabismus surgery
- 330 • Symptoms of diplopia at distance with a frequency of sometimes or worse in primary  
331 position
- 332 • Distance esodeviation of  $2\Delta$  to  $30\Delta$  and distance deviation is at least 1.25 times (25% larger  
333 than) near deviation by PACT (i.e., maximum near deviation is at least 20% smaller than  
334 distance deviation). The distance deviation must exceed the near deviation by at least the  
335 amounts provided in the table below.

336 **PACT Values for DI Eligibility**

Distance Deviation	2	3	4	5	6	7	8	9	10	12	14	16	18	20	25	30
*Max Near Deviation	1	2	3	4	4	5	6	7	8	9	10	12	14	16	20	20

338 Calculation: Distance  $\geq$  Near  $\times 1.25$  or Near  $\leq$  Distance  $\times 0.8$

339 \*Near deviation is the nearest study-permitted prism based on Strabismus Procedures Manual.

- 340 • No more than  $5\Delta$  difference between right and left gaze by PACT
- 341 • No more than  $10\Delta$  difference between primary position and either upgaze or downgaze by  
342 PACT
- 343 • Any coexisting vertical deviation must be less than the distance esodeviation and  $\leq 10\Delta$  by  
344 PACT
- 345 • No paralytic strabismus, paretic strabismus, restrictive strabismus, monocular diplopia,  
346 thyroid eye disease, myasthenia gravis, chronic progressive external ophthalmoplegia, or eye  
347 movement abnormalities associated with known neurological disease. Patients with  
348 Parkinson's disease can be enrolled if non-paretic deviation
- 349 • Visual acuity 20/50 or better in both eyes by ETDRS or Snellen
- 350 • Ability to fuse with prism in space (see section 2.4.2)
- 351 • Investigator is initiating treatment with prism, orthoptic exercises, botulinum toxin injection,  

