### 2.2.1 Eligibility Criteria for CI

485 The following criteria must be met for the subject to be enrolled into the study:

- Adults  $\geq 18$  years of age (adult onset of CI not required)
- No strabismus surgery within the past 10 years
- CI Symptom Survey score  $\geq 21$  points
- Near exodeviation of  $\geq 4\Delta$  and at least  $4\Delta$  larger than at distance by PACT
- Distance exodeviation  $\leq 15\Delta$  by PACT
- Vertical deviation  $\leq 2\Delta$  at distance and near by PACT
- No constant exotropia at distance or near
- Reduced positive fusional vergence (PFV) at near ( $< 20\Delta$  or fails Sheard's criterion that the PFV measures less than twice the magnitude of the near phoria)
- Near point of convergence (NPC) of  $\geq 6$  cm break
- Visual acuity 20/50 or better in both eyes by ETDRS or Snellen
- No paralytic strabismus (e.g., 3rd, 4th, or 6th cranial nerve palsies, skew deviation, Duane syndrome)
- No restrictive strabismus (e.g., blowout fracture, thyroid eye disease, post scleral buckle, Brown syndrome)
- No monocular diplopia
- No paretic strabismus, thyroid eye disease, myasthenia gravis, chronic progressive external ophthalmoplegia, or eye movement abnormalities associated with known neurological disease. Patients with Parkinson's disease can be enrolled if non-paretic deviation.
- No inferior or superior oblique overaction defined as 2+ or greater
- Ability to fuse with prism in space (*see section 2.4.1*)
- Ability to understand and complete a survey
- Investigator is initiating treatment with prism, orthoptic exercises, botulinum toxin injection or surgery

510 • If initiating treatment with botulinum toxin or surgery, planned injection or surgery to be  
 511 within 60 days of enrollment  
 512 • Single treatment modality is planned (e.g., no combined prism and orthoptic exercises)  
 513 • Treatment to be initiated has not been used within the past one year  
 514

515 **2.2.2 Eligibility Criteria for DI**

516 The following criteria must be met for the subject to be enrolled into the study:

517 • Adults  $\geq 18$  years of age  
 518 • Adult-onset DI (at  $\geq 18$  years of age)  
 519 • No prior strabismus surgery  
 520 • Symptoms of diplopia at distance with a frequency of sometimes or worse in primary  
 521 position (in current glasses if wearing glasses)  
 522 • Distance esodeviation of  $2\Delta$  to  $30\Delta$  and distance deviation is at least 1.25 times (25% larger  

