 523 than) near deviation by PACT (i.e., maximum near deviation is at least 20% smaller than  
 524 distance deviation). The distance deviation must exceed the near deviation by at least the  
 525 amounts provided in the table below.

526 **PACT Values for DI Eligibility**

Distance Deviation	2	3	4	5	6	7	8	9	10	12	14	16	18	20	25	30
*Max Near Deviation	1	2	3	4	4	5	6	7	8	9	10	12	14	16	20	20

527 Calculation: Distance  $\geq$  Near  $\times 1.25$  or Near  $\leq$  Distance  $\times 0.8$

\*Near deviation is the nearest study-permitted prism based on Strabismus Procedures Manual.

530

531 • No more than  $5\Delta$  difference between right and left gaze by PACT  
 532 • No more than  $10\Delta$  difference between the primary position at distance and either upgaze or  
 533 downgaze  $\leq 10\Delta$  by PACT  
 534 • Any coexisting vertical deviation must be less than distance esodeviation and  $\leq 10\Delta$  by PACT  
 535 • Visual acuity 20/50 or better in both eyes by ETDRS or Snellen  
 536 • No paralytic strabismus (e.g., 3rd, 4th, or 6th cranial nerve palsies, skew deviation, Duane  
 537 syndrome)  
 538 • No restrictive strabismus (e.g., blowout fracture, thyroid eye disease, post scleral buckle,  
 539 Brown syndrome)  
 540 • No monocular diplopia  
 541 • No paretic strabismus, thyroid eye disease, myasthenia gravis, chronic progressive external  
 542 ophthalmoplegia, or eye movement abnormalities associated with known neurological  
 543 disease. Patients with Parkinson's disease can be enrolled if non-paretic deviation  
 544 • No inferior or superior oblique overaction defined as 2+ or greater  
 545 • Ability to fuse with prism in space (*see section 2.4.2*)  
 546 • Ability to understand and complete a survey  
 547 • Investigator is initiating treatment with prism, orthoptic exercises, botulinum toxin injection  
 548 or surgery  
 549 • If initiating treatment with botulinum toxin or surgery, planned injection or surgery to be  
 550 within 60 days of enrollment  
 551 • Single treatment modality planned (e.g., no combined prism and orthoptic exercises)  
 552 • Treatment to be initiated has not been used within the past one year

553

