- 209 • Frequency of diplopia in reading position during the last week
- 210 • Horizontal deviation at distance (measured using PACT)
- 211 • Horizontal deviation at near (measured using PACT)
- 212 • Whether or not prism was needed to fuse in free space at distance

213

214 The mean, standard deviation, median, and IQR were tabulated for the following:

- 215 • Horizontal deviation at distance (measured using PACT)
- 216 • Horizontal deviation at near (measured using PACT)
- 217 • DQ score
- 218 • Adult-Strabismus (AS-20) general function score
- 219 • AS-20 reading function score
- 220 • AS-20 self-perception score
- 221 • AS-20 interaction score

222

223 **6.4 Secondary Definition of Success: Successful Treatment at Both Distance and**
224 **Near**

225 Successful treatment at both distance and near is defined as diplopia reported “rarely” or
226 “never” both in the reading position and in the distance, and no additional treatment
227 prescribed.

228

229 The following were tabulated by treatment prescribed at enrollment:

- 230 • The number and proportion of participants who met success criteria at both
231 distance and near at 10 weeks
- 232 • The number and proportion of participants who met success criteria at both
233 distance and near at 12 months

234

235 A 95% Clopper-Pearson confidence interval was calculated for each proportion.

236

237 Participants were included in analysis only if the DQ was completed at the visit. There
238 was one exception to this rule. If the treatment history form or the treatment prescribed
239 form at the 10-week visit indicated that additional treatment was received, then the
240 participant will be considered a failure at 12 months. It is acknowledged this procedure
241 may be biased (see Section 4.0).

242

243 **6.5 Successful Treatment within Prism and Surgery Subgroups**

244 The following were tabulated within prism and surgery treatment subgroups:

- 245 • The number and proportion of participants that met success criteria at distance at
246 10 weeks
- 247 • The number and proportion of participants that met success criteria at both
248 distance and near at 10 weeks

- 249 • The number and proportion of participants that met success criteria at distance at
250 12 months
251 • The number and proportion of participants that met success criteria at both
252 distance and near at 12 months
253

254 A 95% Clopper-Pearson confidence interval was calculated for each proportion.
255

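### Motor success is read only at the outcome visit, so surgical patients who enter and stay orthotropic, most plausibly in CI, count as successes and the rate is not a conversion rate

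*Protocol*

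**What the plan says.** Protocol 5.4 sets a secondary objective for each surgery type within a condition: the "proportion of patients with motor success at one year and a 95% confidence interval". Motor "success will be defined as orthotropia by cover/uncover at distance and near fixation in primary" position at one year. For patients who change treatment, the status at the visit of change is carried forward. Missing outcomes in patients who have not changed treatment are multiply imputed. Nothing in the definition refers to status at enrollment. Section 5.5.2 applies the same analysis at 10 weeks.

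The outcome paragraphs of the CI, DI and HT synopses (1.5.1, 1.5.3, 1.5.5) put the question as how often surgical subjects "have become orthotropic at distance and near after treatment".

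Entry (2.2.1 to 2.2.3) depends on deviation size by PACT together with symptoms. CI needs a CISS score of at least 21 and also requires "No constant exotropia at distance or near". Its Sheard criterion is that the "PFV measures less than twice the magnitude of the near phoria". DI and HT need diplopia at least sometimes, with monocular diplopia excluded. No cohort has to show a tropia on cover/uncover or SPCT.

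Cover/uncover, SPCT and PACT are all done at enrollment (2.4.1 to 2.4.3) and repeated at follow-up (3.3).

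**The concern.** To become orthotropic, a patient must first not have been. The rule in 5.4 checks only the end state. PACT measures the whole deviation, latent plus manifest, whereas cover/uncover shows only a manifest one, so a patient can meet the PACT criterion and still be orthotropic on the test that defines success. The CI criteria say as much: they demand a near exodeviation by PACT, forbid a constant exotropia and call the near deviation a phoria.

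The symptom outcome does not have this gap. CI patients enter at a CISS of 21 or more and succeed only below 21 with a gain of at least 9 points. DI and HT patients enter with diplopia at least sometimes and succeed at rarely or never. Nobody can enter as a symptom success. The motor outcome lacks this protection, and the protocol gives no reason for the difference.

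At stake is what the motor proportion means. It mixes patients who converted with patients who had no tropia to correct, and it varies with that mix. Section 1.4 foresees treatment comparisons within conditions to help plan later studies, and a difference in mix between surgery types could pass for a difference in surgical effect.

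**Working it through.** **The plan's own precision figure.** Section 5.2 takes 50 per group with up to 5% loss: 50 × 0.95 = 47.5, stated as about 47. Maximum half-width = 1.96 × √(0.25/47) = 14.3%, which agrees with the stated ±14%. This fixes the scale but does not bear on the definition.

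**Inputs for the effect.** The documents give none of these; all are assumptions.
- f, share orthotropic at both distance and near before surgery: 10% to 50%
- r, probability that such a patient is orthotropic at the outcome visit: 0.8 to 1.0
- c, probability that a patient tropic at entry is orthotropic at the outcome visit: 0.3 to 0.7

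**Formula.** Reported proportion = f·r + (1 − f)·c. Excess over the conversion rate = f·r + (1 − f)·c − c = f(r − c). It is positive whenever r exceeds c.

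**Results at c = 50%.**

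| f | reported, r = 1.0 | reported, r = 0.9 |
|---|---|---|
| 10% | 55% | 54% |
| 20% | 60% | 58% |
| 30% | 65% | 62% |
| 50% | 75% | 70% |

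At f = 20% the excess is 0.20 × (1.0 − 0.5) = 10 points, or 0.20 × (0.9 − 0.5) = 8 points. Over the whole assumed range it runs from 0.10 × (0.8 − 0.7) = +1 point to 0.50 × (1.0 − 0.3) = +35 points.

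**Comparing surgery types.** Two types that both convert 50%, with r = 1.0 but f = 20% and f = 50%, would report 60% and 75%. The 15-point difference is case mix alone.

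**Precision after splitting by baseline status.** The tropic-at-entry row has 47(1 − f) patients: 37.6 at f = 20% (maximum half-width 1.96 × √(0.25/37.6) = 16.0%) and 23.5 at f = 50% (20.2%). At f = 20% the other row has 9.4 patients, with a half-width of about 32%.

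CI groups may be far smaller. Table 1 of the protocol shows 23 CI surgeries a year in the network, 11 of them bilateral medial rectus resection. With n = 11 the maximum half-width is 1.96 × √(0.25/11) ≈ 30%. If 40% were orthotropic at entry (assumed), 6.6 would remain tropic, with a half-width of about 38%. The normal approximation is rough at these sizes.

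**The case against.** The best counter-argument is that an end-state definition is legitimate, that 5.4 is the operative text and that the synopsis phrase is loose. The study is descriptive, the outcome is secondary and limited to surgery, and motor alignment is listed separately in 5.5.1. The protocol also warns, in its background on observational studies and in 1.3, about confounding and patient selection. This limits the weight of the point. It does not make the 5.4 proportion answer the question that three synopses pose, and the general warning about selection does not mention this mechanism.

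Some stronger inferences are tempting and should be resisted:

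- *All three cohorts are equally affected.* The text does not support this. DI and HT require binocular diplopia at least sometimes, which implies a deviation that is manifest at least part of the time. What remains for them is narrower: no criterion requires a tropia on cover/uncover at the enrollment examination.
- *Anyone orthotropic before surgery is a motor success.* Such a patient counts only if also orthotropic at both distances at one year or at the carried-forward visit. A tropia at that visit is a failure.
- *The SAP expects some DI patients to fuse unaided.* SAP 6.3 lists "Whether or not prism was needed to fuse in free space at distance" for tabulation. Listing a variable does not show what was expected of it. The item concerns distance only and is not the cover/uncover result.
- *Restricting the denominator to patients tropic at enrollment gives the unbiased rate.* One cover/uncover examination classifies an intermittent deviation with noise. Some patients caught tropic at entry would look orthotropic later without real change.

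**Conclusion.** The mismatch holds on the text: 5.4 measures how many surgical patients are orthotropic at the outcome visit, not how many became so. It is clearest for CI surgery, where a purely exophoric patient meets the success definition before the operation. For DI and HT it is possible but less likely.

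As a measure of conversion the proportion is too high by f(r − c), provided that r exceeds c. Under the assumed f = 20%, c = 50% and r = 0.9 to 1.0 this is +8 to +10 points. A reader might infer a known or large bias, but the documents contain no value for f, r or c, so the size cannot be established from them. The primary symptom outcome is unaffected. The SAP supplied covers DI only and contains no motor-success analysis, so it neither resolves the point nor needs rewording on it.

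**What to change.** In Protocol 5.4, and through 5.5.2 at 10 weeks, report motor success for each surgery type by cover/uncover status at the examination that serves as baseline:

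- one row for patients tropic at distance or near, labelled *became orthotropic*;
- one row for patients orthotropic at both, labelled *remained orthotropic*, described with their change in PACT.

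Keep the overall proportion, labelled *orthotropic at one year*. State that it is not a conversion rate and is not to be compared across surgery types without the baseline split. Carry the same layout into any analysis plan that reports motor success. Even with the split, comparisons between surgery types remain open to the confounding that the protocol already acknowledges.

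No new data are needed. The costs are wider intervals within rows, most of all in the small CI surgery groups, and a baseline split that is noisy for intermittent deviations. A footnote should say so, and neither row should be presented as free of bias.

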#### 975 **5.5 Additional Analyses**

976 **5.5.1 Secondary Outcomes at One Year**

977 Secondary outcomes at one year will be evaluated within each modality/condition. Secondary  
978 outcomes to be assessed include motor alignment, near point of convergence (CI only), positive  
979 fusional vergence (CI only), negative fusional vergence (DI only), vertical fusional vergence (HT  
980 only), and the Adult Strabismus 20 (AS-20) questionnaire. In addition, mean CI Symptom  
981 Survey (CISS) score will be evaluated for CI, and the AS-20 and Diplopia Questionnaire will be  
982 evaluated as a continuous outcomes for all three conditions.

983

#### 984 **5.5.2 Outcomes at 10 Weeks**

985 Outcomes at the 10-week interim visit will be evaluated similarly to the primary and secondary  
986 analyses defined for one-year time points (*sections 5.3, 5.4 and 5.5.1*).

987

988

1
2
3
4
5
6
7
8
9
10
11
12
13

**Study of Adult Strabismus (SAS1)
Treatment and Outcomes in Subjects Enrolled with Divergence Insufficiency**

**Statistical Analysis Plan
Version 1.0**

Statistical Analysis Plan Version: 1.0, 04Jun2020
Protocol Version: 2.0, 11Apr2016

VERSION HISTORY

The following table outlines changes for the analysis plan:

VERSION NUMBER	AUTHOR	APPROVER	EFFECTIVE DATE	REVISION DESCRIPTION
1.0	[name]	[name]	04Jun2020	The statistical analysis plan was started prior to the analysis of data but was completed after an initial draft of the manuscript was written.

14
15
16
17
18
19
20
21
22
23

Signature of author: _____

Signature of approver: _____

24 **1.0 Overview**

25

26 **1.1 Study Synopsis**

27 Adults diagnosed with divergence insufficiency (DI) were enrolled if eligibility criteria
28 were met and one of the following treatments (subsequently referred to as treatment
29 modalities) were prescribed at the enrollment visit: Botox, orthoptic exercises, prism, or
30 surgery. The prescription of treatment for strabismus was at investigator discretion and
31 was used to identify eligible participants. Treatment assignment was not part of the
32 protocol.

33

34 **1.2 Manuscript Objective**

35 This study was designed to accomplish two study objectives:

- 36 • To describe clinical characteristics, symptoms, and prescribed treatments of adults
37 diagnosed with DI at enrollment
- 38 • To characterize symptoms and clinical outcomes at 10 weeks and 12 months after
39 the initiation of treatment

40

41 **1.3 Primary Outcome: Treatment Success**

42 The primary outcome is the proportion of participants who met success criteria. Success
43 is evaluated at 10 weeks and at 12 months after treatment was initiated.

44

45 At each timepoint, participants were classified as successfully treated if **all** the following
46 criteria were met:

- 47 • Participant indicated on the diplopia questionnaire (DQ) that diplopia in the
48 distance was experienced “rarely” or “never” during the last week
- 49 • Additional treatment (defined in section 4.0) was NOT received prior to the office
50 visit

51

52 **2.0 Treatment at Enrollment**

53 Participants were eligible for the study if one of four treatments was initiated at the
54 enrollment visit:

- 55 1. Botox injection
- 56 2. Newly prescribed orthoptic exercises
- 57 3. Newly prescribed prism
- 58 4. Surgery

59

60 Newly Prescribed Prism

61 Participants who received newly prescribed prism were further categorized into the
62 following subgroups, based on the amount (percent) of the underlying deviation that was
63 corrected by the prism prescribed at enrollment:

- 64 • Low relieving prism (0 to <60% of underlying deviation corrected)
- 65 • High relieving prism (60 to <100% of underlying deviation corrected)
- 66 • Correcting prism (\geq 100% of underlying deviation corrected)

67

68 The percent of the deviation corrected by prism at enrollment is defined as

69 $\frac{\text{total prism prescribed at enrollment}}{\text{magnitude of distance deviation}} \times 100$, where

- 70 • Total prism prescribed at enrollment is defined as the sum of the prism
- 71 prescriptions in the left and right eyes at enrollment
- 72 • Magnitude of distance deviation is the size of the distance deviation measured by
- 73 prism and alternate cover test (PACT)

74

75 Surgery

76 Participants who received surgery were further categorized into the following groups
77 based on the type of surgery performed:

- 78 • Bilateral medial rectus recession
- 79 • Bilateral lateral rectus resection
- 80 • Other including:
 - 81 ○ Bilateral medial rectus muscle recession, superior rectus muscle nasal pole
 - 82 recession
 - 83 ○ Bilateral medial rectus muscle recession, superior rectus muscle recession
 - 84 ○ Bilateral lateral rectus muscle resection with superior transposition
 - 85 ○ Bilateral medial rectus muscle recession with superior transposition
 - 86 ○ Lateral rectus muscle tuck/plication, superior rectus muscle recession
 - 87 ○ Medial rectus muscle recession, lateral rectus muscle resection
 - 88 ○ Single medial rectus muscle recession
 - 89 ○ Single lateral rectus muscle tuck/plication

90

91 **3.0 Re-enrollment**

92 Participants enrolled into the prism and orthoptic exercises groups were given the option
93 to re-enroll into the study if Botox or strabismus surgery was prescribed at the 10-week
94 or 12-month office visit, and all other eligible criteria were met.

95

96 For participants who were re-enrolled following the prescription of strabismus surgery at
97 the 10-week visit, the 10-week visit served as both the outcome visit for the initial
98 treatment (prism or orthoptic exercises) and the enrollment visit for the second treatment
99 (Botox or strabismus surgery). Similarly, for participants who were re-enrolled at the 12-
100 month visit, the 12-month visit served as both the outcome visit for the initial treatment
101 and the enrollment visit for second treatment.

102

103 When data are analyzed, participants who were re-enrolled may contribute two outcomes
104 to the analysis, one reflecting the results of prism treatment or orthoptic exercises, which
105 was the initial prescribed treatment, and the other reflecting the results of strabismus
106 surgery or Botox injection, which was received after the participant was re-enrolled. Even
107 though some participants may contribute multiple outcomes to the analysis, there will be
108 no adjustment for the potential correlation between these outcomes. Botox and strabismus
109 surgery result in permanent changes to the ocular system and are not expected to be
110 influenced by prior treatment with orthoptic exercises or prism. Therefore, it is safe to
111 assume that outcomes collected for the initial treatment are independent of outcomes
112 collected after re-enrollment.

113

114 **4.0 Additional or Newly Initiated Treatment during Follow Up**

115 Investigators were encouraged to observe enrolled participants for 12 months before
116 initiating new treatment. However, given that this is an observational study, investigators
117 were not limited in their ability to change existing treatment or to initiate new treatment.
118 In a general sense, treatment prescribed after enrollment may be classified as “additional
119 treatment” (also referred to as “newly initiated treatment”), but this definition depends on
120 the treatment initiated at enrollment and the timing of the newly initiated treatment.
121 Below are definitions of additional treatment.

122 Prism group

123 Participants enrolled following the prescription of prism were considered to have
124 received additional treatment at 10 weeks if the treatment history form at 10 weeks
125 indicated that Botox, orthoptic exercises, or surgery was received prior to the office visit.
126 At 12 months, participants were considered to have received additional treatment if the
127 treatment prescribed form at 10 weeks or the treatment prescribed form at 12 months
128 indicated that Botox, orthoptic exercises, or surgery was prescribed or received.

129
130
131 When evaluating treatment success within prism subgroups (low-relieving prism, high-
132 relieving prism, correcting prism), the prism prescription at follow-up was taken into
133 consideration as well. In addition to the definition provided above, participants were
134 considered to have received additional treatment if there was an increase in the prism
135 prescription after enrollment. Participants were considered to have received additional
136 treatment at 10 weeks if the treatment history form at 10 weeks indicated that the
137 magnitude of the prism prescription had increased since enrollment. Participants were
138 considered to have received additional treatment at 12 months if the treatment prescribed
139 form at 10 weeks or the treatment history form at 12 months indicated that the magnitude
140 of prism prescribed had increased since enrollment.

141 Surgery group

142 Participants who were prescribed surgery at enrollment were considered to have received
143 additional treatment if the treatment history form at 10 weeks indicated that Botox or
144 surgery was received prior to the office visit. Participants were considered to have
145 received additional treatment at 12 months if the treatment prescribed form at 10 weeks
146 or the treatment history form at 12 weeks indicated that Botox, orthoptic exercises, prism,
147 or surgery was prescribed or received.

148 **5.0 Primary Analysis**

149 The following were tabulated by treatment prescribed at enrollment:

- 150 • The number and proportion of participants who met success criteria at distance
151 (see Section 1.3) at 10 weeks
- 152 • The number and proportion of participants who met success criteria at distance
153 (see Section 1.3) at 12 months

154 A 95% Clopper-Pearson confidence interval was calculated for each proportion.

159 Participants were included in analysis only if the DQ was completed at the visit. There
160 was one exception to this rule, participants were considered a failure if additional
161 treatment was received prior to the visit. If the 10-week treatment history form indicated
162 that additional treatment was received prior to the 10-week visit, the participants was
163 considered a failure both at 10 weeks and at 12 months. If the 12-month treatment history
164 form or the 10-week treatment prescribed form indicated that additional treatment was
165 received prior to the 12-month visit, then the participant was considered a failure at 12
166 months. When additional treatment was received prior to the visit, the participant was
167 counted in the denominator but not the numerator when calculating the success
168 proportion. It is acknowledged that this procedure is biased unless the 10-week and 12-
169 month DQ data are not missing at random (NMAR), with those who missed that visit
170 being in truth more likely to be failures than those who completed the visit. In that case,
171 this procedure may be less biased. If the data are missing completely at random (MCAR),
172 the resulting estimate of success is an underestimate.

173

174 **6.0 Secondary Analyses**

175 Data collected after additional treatment was received was no longer representative of the
176 treatment initiated at enrollment. Consequently, data were excluded from analyses and
177 tabulations if additional treatment was prescribed or received prior to the visit, unless
178 otherwise specified.

179

180 **6.1 Number and Proportion of Participants that Received Each Treatment**

181 The number and proportion of participants that were prescribed each treatment at
182 enrollment was tabulated. Participants who were re-enrolled will be counted twice: once
183 for the initial treatment (orthoptic exercises or prism) prescribed at enrollment and again
184 for the second treatment (Botox or surgery), prescribed at re-enrollment.

185

186 **6.2 Participant characteristics at Enrollment and Medical History**

187 The following characteristics reported at enrollment were tabulated according to the
188 treatment initiated at enrollment:

189

- 190 • Sex
- 191 • Race/Ethnicity (White versus non-White)
- 192 • Age (18-24, 25-34, 35-44, ..., 75-84, 85-91)
- 193 • Whether or not refractive correction (spectacles or contact lenses) was
194 worn at the office visit
- 195 • Prior treatment for strabismus (orthoptic exercises, prism, none)
- 196 • Coexisting neurological conditions (Parkinson's, progressive supranuclear
197 palsy, basal ganglia disease, stroke, intracranial tumor)
- 198 • Other conditions (epiretinal membrane; age-related macular degeneration;
199 macular pathology; heart disease; diabetes; autoimmune disease;
200 significant head trauma; hypertension; cancer of bladder, breast, or
201 prostate)

201

202 The mean, standard deviation, median, and interquartile range (IQR) will be calculated
203 for age at enrollment.

204

205 **6.3 Clinical Characteristics at Enrollment**

206 The following clinical characteristics measured at enrollment were tabulated according to
207 the treatment initiated at enrollment:

- 208 • Frequency of diplopia at distance during the last week
- 209 • Frequency of diplopia in reading position during the last week
- 210 • Horizontal deviation at distance (measured using PACT)
- 211 • Horizontal deviation at near (measured using PACT)
- 212 • Whether or not prism was needed to fuse in free space at distance

213

214 The mean, standard deviation, median, and IQR were tabulated for the following:

- 215 • Horizontal deviation at distance (measured using PACT)
- 216 • Horizontal deviation at near (measured using PACT)
- 217 • DQ score
- 218 • Adult-Strabismus (AS-20) general function score
- 219 • AS-20 reading function score
- 220 • AS-20 self-perception score
- 221 • AS-20 interaction score

222

223 **6.4 Secondary Definition of Success: Successful Treatment at Both Distance and**
224 **Near**

225 Successful treatment at both distance and near is defined as diplopia reported “rarely” or
226 “never” both in the reading position and in the distance, and no additional treatment
227 prescribed.

228

229 The following were tabulated by treatment prescribed at enrollment:

- 230 • The number and proportion of participants who met success criteria at both
231 distance and near at 10 weeks
- 232 • The number and proportion of participants who met success criteria at both
233 distance and near at 12 months

234

235 A 95% Clopper-Pearson confidence interval was calculated for each proportion.

236

237 Participants were included in analysis only if the DQ was completed at the visit. There
238 was one exception to this rule. If the treatment history form or the treatment prescribed
239 form at the 10-week visit indicated that additional treatment was received, then the
240 participant will be considered a failure at 12 months. It is acknowledged this procedure
241 may be biased (see Section 4.0).

242

243 **6.5 Successful Treatment within Prism and Surgery Subgroups**

244 The following were tabulated within prism and surgery treatment subgroups:

- 245 • The number and proportion of participants that met success criteria at distance at
246 10 weeks
- 247 • The number and proportion of participants that met success criteria at both
248 distance and near at 10 weeks

- 249 • The number and proportion of participants that met success criteria at distance at
250 12 months
251 • The number and proportion of participants that met success criteria at both
252 distance and near at 12 months
253

254 A 95% Clopper-Pearson confidence interval was calculated for each proportion.
255

256 Participants were included in analysis only if the DQ was completed at the visit. There
257 was one exception to this rule: participants were considered a failure if additional
258 treatment was received prior to the visit. It is acknowledged this procedure may be biased
259 (see Section 5.0).
260

261 **6.6 Secondary Clinical Outcomes**

262 The following statistics will be calculated to describe the DQ score and each AS-20
263 subscale score at each visit, according to the treatment initiated at enrollment:

- 264 • Mean score at visit and standard deviation
265 • Mean change in score from enrollment and the corresponding 95% confidence
266 interval
267

268 These statistics were also calculated according to treatment subgroups.
269

270 **6.7 Treatment Success for Participants Enrolled into the Surgery Group by 271 Whether Prism was Prescribed Prior to Enrollment or No Prior Treatment was 272 Reported**

273 The following were tabulated for participants who were prescribed surgery at enrollment
274 according to whether prism was prescribed prior to enrollment or no treatment was
275 prescribed prior to enrollment:

- 276 • The number and proportion of participants that met success criteria at distance at
277 10 weeks
278 • The number and proportion of participants that met success criteria at both
279 distance and near at 10 weeks
280 • The number and proportion of participants that met success criteria at distance at
281 12 months
282 • The number and proportion of participants that met success criteria at both
283 distance and near at 12 months
284

285 A 95% Clopper-Pearson confidence interval was calculated for each proportion.
286

287 Participants were included in analysis only if the DQ was completed at the visit. There
288 was one exception to this rule: participants were considered a failure if additional
289 treatment was received prior to the visit. It is acknowledged this procedure may be biased
290 (see Section 5.0).
